9.2 Antibodies

Anti-somatrogon antibody (ADA), anti-somatrogon neutralizing antibody, and anti-hGH neutralizing antibody will be tested at month six and month 12 in Period III and then every six months thereafter. The results of the antibody testing will be summarized for each test at each of the OLE and PEN time points tested. The titer and specificity (anti-hGH and CTP) of confirmed ADA will be summarized. The anti-somatrogon and anti-hGH neutralizing antibody status (positive or negative) are only assessed when a patient is confirmed positive for ADA, so any sample that has not shown somatrogon specificity will be considered negative for NAb. The numeric values for titer will be summarized by median, min and max.

Overall incidence of TEAEs and injection site reactions will also be summarized by ADA status.

HV, HT SDS, and peak IGF-1 SDS will be summarized for each reporting period by ADA status.

ADA status will be assigned on a rolling or dynamic basis. A patient is only considered ADA positive at the beginning of the year in which they test positive and for the remainder of the study.

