Patients who received active comparator, Genotropin, during the Main Study, will be switched to MOD-4023 (will be randomized to one of the three MOD-4023 cohorts). Their visit schedule during the first three months of the OLE will be as follows: Visit 1 OLE for the first MOD-4023 injection and training of MOD-4023 administration (week 52 +1 day, which is

OPKO Biologics	Protocol for Clinical Study CP-4-004	Page 58 of 133
Effective Date: Date of final electronic approval		

on Month 12 visit of the Main Study), Visit 2 OLE will be 28 days + 4 (-1) days after the first MOD-4023 injection and Visit 3 OLE will be 3 months after first MOD-4023 injection (i.e. 13±2 weeks + 4 (-1) days after the first MOD-4023 injection). All subsequent visits will be every three months (i.e. every 13±2 weeks, 4 days (or 3 days, when necessary) after dosing).

Patients who are off treatment for over XXXXXXXXXX between the last MOD-4023/Genotropin dose in the Main Study and the first OLE dose (2nd year) will be allowed to continue into the OLE period after the following tests will be conducted:

- Parameters of glucose metabolism: fasting glucose, insulin, and HbA1c
- Antigenicity: anti MOD-4023 antibodies (only Genotropin group – baseline for future tests)
- Routine safety laboratory (biochemistry, hematology, and urinalysis)
- PD: IGF-I and IGFBP-3 baseline serum levels
- MOD-4023 baseline serum levels

In the 12-month OLE visit (the second year of treatment) the following assessments will be included at each visit (unless otherwise specified):

- Adjustment of dose for weight
- local tolerability
- Physical examination and vital signs;
- AEs, and concomitant medications;
- Parameters of glucose metabolism: fasting glucose, insulin, and HbA1c;
- Other hormonal levels: TSH, free T4, free T3, cortisol;
- Antigenicity: anti MOD-4023 antibodies (only once every 6 months);
- Routine safety laboratory (biochemistry, hematology, and urinalysis);
- Patient's height;
- Patient's weight;
- Parameters of lipid metabolism;
- Lp(a) lipoprotein (only once at Month 12 OLE);
- Pubertal status (only once at Month 12 OLE);
- PD: IGF-I and IGFBP-3 serum levels;
- MOD-4023 serum levels;
- Fundoscopy (once at Month 12 OLE, or earlier if there are signs or symptoms indicative of benign intracranial hypertension);
- ECG (only once at Month 12 OLE)

OPKO Biologics	Protocol for Clinical Study CP-4-004	Page 59 of 133
Effective Date: Date of final electronic approval		

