The following assessments will be conducted every 6 months (± 2 weeks) on day 4 (-1) post dose on top of the 3 month assessments:

- IGF-I, IGFBP-3 and MOD-4023 serum levels.
- Once a year, patients will be required to attend another visit **on dosing day** (in addition to the semi-annual visit on day 3 or 4 post dosing) where the following additional assessments will be conducted (on top of the three and six months assessments):Anti-MOD-4023 antibodies;
- MOD- 4023 serum levels
- Physical examination;
- Vital signs;
- Parameters of glucose metabolism (fasting glucose, fasting insulin and HbA1c);
- Other hormonal levels (TSH, free T4, free T3, cortisol);
- Parameters of lipid metabolism;
- Routine safety laboratory (biochemistry, hematology and urinalysis);
- Pubertal status;
- ECG;
- Bone age;
- For males above the age of 13 - LH, FSH and testosterone. For females above the age of 12 - LH, FSH and estradiol;
- Fundoscopy (if indicated).

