Auxology measurements: Actual height measured on a calibrated stadiometer and body weight measurement		X	X		X	X	X	X
Adjustment of dose for weight			X		X	X	X	X
AEs			X		X	X	X	X
Local tolerability			X		X	X	X	X
Concomitant medication		X	X		X	X	X	X
Dispensing of drug					X	X	X	X
IGF-I, IGFBP-3 and MOD-4023 serum levels	X	X	X		X			X
MOD-4023 serum levels			X					X
Anti-MOD-4023 antibodies	X	X	X					X
Physical examination		X	X					X
Vital signs		X	X					X
Glucose metabolism (fasting glucose & insulin, HbA1c)	X	X	X					X
Other hormonal levels (TSH, free T4, free T3, cortisol)			X					X

¹ Applicable only to patients who were off-treatment for over 60 days between OLE Month 12 and Visit 1 LT-OLE.

² This visit applies only to patients in Cohorts 1 and 2 who switch to MOD-4023 0.66 mg/kg/week; this will be their first visit after the switch. Selected group of patients may be switched during the 2nd year and will be required to undergo this visit three months after their switch.

³ This visit applies to patients who discontinue the study prematurely for any reason (including not switching to higher dose).

OPKO Biologics	Protocol for Clinical Study CP-4-004	Page 115 of 133
Effective Date: Date of final electronic approval		

	follow up Visit ¹	First Month 3 visit ² (on day 3 or 4 post- dosing)	Early termination visit ³	LT OLE visits by Month over each year until switch to LT- OLE-PEN period			
				Month 3 visit	Month 6 visit	Month 9 visit	Month 12 each year and End of Study Visit
Parameters of lipid metabolism			X				X
Routine safety laboratory (biochemistry, hematology and urinalysis)	X	X	X				X
Pubertal status			X				X
ECG			X				X
Bone age			X				X
LH, FSH and Testosterone ⁴			X				X
LH, FSH and Estradiol ⁵			X				X
Patient diary dispensing and return of completed diaries				X	X	X	X

⁴ For male patients that are at the age of 13 years and above.

⁵ For female patients that are at the age of 12 years and above.

OPKO Biologics	Protocol for Clinical Study CP-4-004	Page 116 of 133
Effective Date: Date of final electronic approval		

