Appendix 4: Schedule of Assessments – Long-Term OLE PEN (LT-OLE-PEN) Period V first year

Assessments	PEN Visit 1 (PEN V1)	PEN Visit 2 (PEN V2) 4 weeks (+1) after PEN visit V1	LT OLE PEN visits by Month over the first year			
			Month 3 visit (±2 week)	Month 6 visit (±2 week)	Month 9 visit (±2 week)	Month 12 (±2 week) ¹
Informed consent/ assent	X					
Auxology measurements (actual height measured on calibrated stadiometer)	X		X	X	X	X
Body Weight measurement	X	X	X	X	X	X
Adjustment of dose for weight	X	X	X	X	X	X
AEs	X	X	X	X	X	X
Local tolerability	X	X	X	X	X	X
Concomitant medication	X		X	X	X	X
Dispensing of drug	X	X	X	X	X	X
Return of used drugs	X ²	X	X	X	X	X
Training on PEN	X	X ³				
Fundoscopy- If required	X	X	X	X	X	X
IGF-I, IGFBP-3	X	X	X	X	X	X
MOD-4023 serum levels	X	X	X	X	X	X
Anti-MOD-4023 antibodies	X	X	X	X	X	X
Physical examination	X	X	X	X	X	X
Vital signs	X	X	X	X	X	X
Glucose metabolism (fasting glucose & insulin, HbA1c)	X		X	X		X
Other hormonal levels (TSH, free T4, cortisol)	X		X	X		X
Parameters of lipid metabolism	X		X	X		X
Routine safety laboratory (biochemistry, hematology and urinalysis)	X		X	X		X
Urine pregnancy test ⁴	X	X	X	X	X	X

¹ In case ET/EOS visit is conducted all assessment should be done at one visit with no split.

² Return of used and unused MOD-4023 vials.

³ If required.

⁴ For females of child bearing potential. In case urine pregnancy test is positive, please refer to section [7.4](#) in the protocol.

OPKO Biologics	Protocol for Clinical Study CP-4-004	Page 117 of 133
Effective Date: Date of final electronic approval		

	PEN Visit 1 (PEN V1)	PEN Visit 2 (PEN V2) 4 weeks (+1) after PEN visit V1	LT OLE PEN visits by Month over the first year			
			Month 3 visit (±2 week)	Month 6 visit (±2 week)	Month 9 visit (±2 week)	Month 12 (±2 week) ¹
Pubertal status ¹	X		X	X	X	X
ECG around Tmax (7-12 hours post dose) ²						X
Bone age	X ³					X
LH, FSH and Testosterone ⁴	X					X
LH, FSH and Estradiol ⁵	X					X
Provide patient diary and return of completed diaries		X	X	X	X	X

¹ In case the patient becomes pubertal, childbearing potential and refraining from sexual activity will be discussed with the patient.

² In case not possible to conduct the ECG around Tmax at the 12 months visit, it can be performed on month 12± 3 weeks (7-12 hours post dose).

³ Bone age measurement will be performed in case the previous assessment was done more than 6 months prior to this visit.

⁴ For male patients that are at the age of 13 years and above.

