4.3 Study Flow Chart OLE (Periods III, IV, V)

Period III (starting 2nd year of treatment, i.e. first year OLE)

OLE	Day 1 and Month 1 OLE ¹	Every 3 months OLE visit	Every 6 months OLE visit	Every 12 months
	Visits 1-2			
Previous and concomitant medication	Х	Х		
Actual HT	Х	Х		
Body weight	X	Х		
Physical examination	Х	Х		
Vital signs	Х	Х		
Injection site reaction (local tolerability)	Х	X		
ECG				X
Pubertal status (Tanner)				X
BA (Greulich-Pyle)				Х
Routine safety biochemistry/ hematology and urinalysis	Х	X		
IGF-I and IGFBP-3	X	X		
Somatrogon serum levels	X	X		
Anti-somatrogon antibodies			X	
Thyroid status (FT4, T3, TSH)	X	Х		
Cortisol levels	X	Х		
Fasting glucose, fasting insulin	X	Х		
HbA1c	Х	Х		
Lipid panel	X	X ²		
Lipoprotein				Х
AE assessment	Х	Х		
Fundoscopy ²				X ²
Somatrogon administration	X			
Training for study medication administration	Х			
Dispense study medication	X	X		
Dispense patient diary	X	X		
Return and accountability of study medication	Х	X		
Return and review of patient diary	X	X		

¹ Only patients who received Genotropin in the main study and switched to somatorogon will attend these 2 visitsapplicable only for first year of extension

² Earlier if there are clinical signs of intracranial hypertension

Periods IV (Treatment with 0.66 mg/kg)

OLE	Every 3 months OLE visit - day 4 (-1) post dose	Every 6 months OLE visit – day 4 (-1) post dose	Every 12 months OLE and EOS when marketing approval received - on dosing day
Auxology measurements: Actual HT measured on a calibrated stadiometer and body weight measurement	Х		
Adjustment of dose for weight	Х		
AEs	Х		
Local tolerability	Х		
Concomitant medication	Х		
Dispensing of drug	Х		
IGF-1, IGFBP-3 and somatrogon serum levels		Х	
Anti-somatrogon antibodies			X
Physical examination			X
Vital signs			X
Parameters of glucose metabolism (fasting glucose, fasting insulin and HbA1c)			Х
Other hormonal levels (TSH, FT4, T3, cortisol)			X
Parameters of lipid metabolism			Х
Routine safety laboratory (biochemistry, hematology and urinalysis)			Х
Pubertal status			Х
ECG			Х
BA			X
Lutinizing hormone (LH), follicle stimulating hormone (FSH) and testosterone. ³			Х
LH, FSH and estradiol ⁴			X

³ For male patients that are on the age 13 years old and above ⁴ For female patients that are at the age of 12 years old and above

Period V LT-OLE PEN – First 12 Months

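### The SAP's six-monthly antibody schedule is wrong for Period IV and the first PEN year, so any-positive counts can rise on PEN from extra testing alone

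*SAP*

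**What the plan says.** SAP Section 9.2 states that ADA and the two neutralizing-antibody tests "will be tested at month six and month 12 in Period III and then every six months thereafter". It then plans a summary at each time point tested. It also defines a rolling ADA status: a positive test makes the patient positive from the start of that year to the end of the study.

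The schedules are as follows.

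- **Period III.** Protocol Section 5.2: "Antigenicity: anti MOD-4023 antibodies (only once every 6 months". This agrees with Section 9.2.
- **Period IV.** Protocol Section 5.3: "Once a year, patients will be required to attend another visit" on a dosing day, "where the following additional assessments will be conducted (on top of the three and six months assessments):Anti-MOD-4023 antibodies". The six-monthly list in that section has IGF-I, IGFBP-3 and drug levels but no antibodies. Protocol Appendix 3 agrees. The Period IV chart in SAP Section 4.3 marks antibodies only in the column "Every 12 months OLE and EOS when marketing approval received - on dosing day".
- **Post-switch sample.** Section 5.3 and Appendix 3 add an antibody sample at a visit three months after the switch to 0.66 mg/kg/week. Appendix 3, footnote 2: "This visit applies only to patients in Cohorts 1 and 2 who switch to MOD-4023 0.66 mg/kg/week".
- **First PEN year.** Protocol Section 5.4.1 and Appendix 4 list antibodies at PEN V1 (before dosing), PEN V2 and months 3, 6, 9 and 12. The SAP chart marks them every three months and has no column for V1 or V2.
- **From the second PEN year.** Months 6 and 12 in both documents.

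SAP Section 9.1 makes the presence of an anti-somatrogon or neutralizing antibody a criterion for the immunogenicity AE of special interest (AESI). AE rates are reported for each year and cumulatively on PEN, over the number of patients at the start of the year or period. Table 14.3.2.5 gives the AESIs annually and Table 20 gives them for the PEN years.

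**The concern.** Safety is the primary objective of the extension analysis, and antibody incidence is the second safety endpoint in SAP Section 3.2.1. Sampling is sparsest in Period IV and densest just after the move to the PEN product. An output that counts a patient once for any positive in an interval gives each child more chances to be counted in the first PEN year than in the year before. Section 9.2 hides this by describing an even schedule, and no rule in the SAP allows for unequal testing. A reader who sets the annual tables beside the PEN tables could take a rise for immunogenicity of the PEN product. The rolling status carries the same imbalance into the growth and safety tables split by ADA status, because a child whose intermittent positivity was missed in Period IV may first become ADA-positive on PEN.

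**Working it through.** **Step 1. Count scheduled antibody samples per 12 months.**

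| Interval | SAP 9.2 text | Protocol | SAP 4.3 chart |
|---|---|---|---|
| Period III | 2 | 2 | 2 |
| Period IV, routine | 2 | 1 | 1 |
| Period IV, switch year, Cohorts 1 and 2 | 2 | 1 + 1 = 2 | 1 (extra visit not shown) |
| PEN year 1 | 2 | 6, of which 6 − 1 = 5 follow the first PEN dose | 4 |
| PEN year 2 onward | 2 | 2 | 2 |

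The figure of two a year is reproduced for Period III and from PEN year 2. It fails for routine Period IV and for PEN year 1. In the switch year the total for Cohorts 1 and 2 happens to be two, but one sample is tied to the switch. If the switch falls at a month 9 visit, Section 5.3 puts the follow-up on a dosing day, where it appears to coincide with the yearly visit. Off-treatment follow-up and early-termination visits add samples for some patients.

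**Step 2. How much could the number of samples matter?** The documents give neither a positivity rate nor a duration, so both are assumed here.

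*(a) Fully transient positivity.* If each sample is independently positive with probability p, the chance of at least one positive in k samples is 1 − (1 − p)^k.

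| p | k = 1 | k = 2 | k = 4 | k = 5 | k = 6 |
|---|---|---|---|---|---|
| 2% | 2.0% | 4.0% | 7.8% | 9.6% | 11.4% |
| 5% | 5.0% | 9.8% | 18.5% | 22.6% | 26.5% |
| 10% | 10.0% | 19.0% | 34.4% | 41.0% | 46.9% |
| 20% | 20.0% | 36.0% | 59.0% | 67.2% | 73.8% |

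For p = 5% and k = 5: 1 − 0.95^5 = 1 − 0.774 = 0.226, which is 4.5 times the one-sample figure. Across p = 2% to 20% the ratio of five samples to one runs from 4.8 down to 3.4. For scale, among the 53 patients who started the OLE, p = 5% gives 53 × 0.05 = 2.7 patients with one sample and 53 × 0.226 = 12.0 with five. The number who move to PEN is not stated. Positive correlation between samples from the same child lowers these figures, so they are upper limits for each p.

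*(b) Episodes of fixed length.* Let one positive episode of d months start uniformly within the year. It is caught if some sample month t satisfies s ≤ t ≤ s + d, where s is the start.

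| d | Month 12 only | Months 6, 12 | Every 3 months | Week 4 and every 3 months |
|---|---|---|---|---|
| 1 month | 8% | 17% | 33% | 42% |
| 3 months | 25% | 50% | 100% | 100% |
| 6 months | 50% | 100% | 100% | 100% |
| 12 months | 100% | 100% | 100% | 100% |

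With d = 1, the yearly sample catches 1/12 and the five on-PEN samples catch 5/12. With d = 12 the schedules do not differ.

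**Step 3. Which outputs are exposed?** Results at a single time point do not depend on how many other samples fall in the year. The rolling ADA status in Section 9.2 and the immunogenicity AESI in Section 9.1 do, because one positive anywhere in the interval is enough. The start-of-period denominator also does not show how many patients were tested.

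**The case against.** The strongest reply is that this is one wrong sentence with little consequence. Section 9.2 already plans results at each time point, so Month 12 can be read separately, and titers are listed by patient. PEN V1 is sampled before dosing and serves as the Period V baseline, so positivity that predates PEN can be separated. All of that stands.

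Several stronger readings are tempting and are not supported.

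- **Biased yearly incidence tables.** Tables 6 and 14.4.1 are titer tables, and Section 9.2 summarizes titer by median, minimum and maximum. They cannot be read as yearly incidence tables that assume even testing.
- **A biased vial-versus-PEN or cohort comparison.** The SAP plans neither for antibodies and tests no hypotheses. After the first OLE year it pools all patients. Its tables crossing ADA status with initial cohort report growth. Protocol Section 8.5 does ask for an antibody summary by cohort, so the post-switch sample matters if one is produced.
- **Six samples in the SAP's first PEN year.** Six is the protocol's count. The SAP chart gives four, which is a further mismatch between the two.

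A last objection concerns the repair. A Month 12 sample is not assured, because SAP Section 4 lets PEN transition fall at any study month and the last Period IV year may be cut short. Month 12 is also not at a fixed time after dosing: day 3 or 4 in Period III, dosing day in Period IV and PEN year 1, and day 4 (−1) from PEN year 2. Both points are right and shape the fix.

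**Conclusion.** The inconsistency is certain: Section 9.2 is contradicted for Period IV by the protocol and by the SAP's own chart, and for the first PEN year by both documents. The consequence is conditional. Any-positive ADA status and immunogenicity AESI counts can rise in the first PEN year from more frequent testing alone if positivity is transient or intermittent. Under assumed per-sample rates of 2% to 10%, five samples give at most 9.6% to 41% any-positive, against 2% to 10% with one. The effect is nil for antibodies that last a year or more, and the documents do not say which case applies. A reader might infer that antibody incidence simply tracks the number of tests, but that would need transient positivity, which nothing in the plan establishes. The correction should be made because it is cheap and bears on a named safety endpoint.

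**What to change.** 1. Replace the sentence in SAP Section 9.2 with the actual schedule for each period, including the post-switch sample and the off-treatment and early-termination samples.
2. Reconcile the SAP's first PEN year chart with protocol Appendix 4, which has V1 and V2 samples that the chart lacks.
3. For antibody incidence by year and on PEN, including the immunogenicity AESI, use patients tested as the denominator and show the number of samples per patient. SAP Section 9.4 already uses patients with results as its denominator for IGF-1 SDS at each visit.
4. Add a common-sample row based on Month 12, with the pre-dose PEN V1 sample standing in where the last Period IV year has no Month 12. Footnote which samples fall on dosing day and which on day 3 or 4.
5. Count on-PEN positivity only from samples taken after PEN V1.
6. Flag the post-switch Month 3 sample in any antibody summary by cohort.

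The cost is SAP wording and one or two extra table rows. No new samples or visits are needed.

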5.7.1.5 Assessment of antigenicity

Immunogenicity of MOD-4023 and of r-hGH will be assessed.

Baseline data for anti-hGH will be collected at Screening, and no patients with positive anti-hGH antibodies will be included in the study. Baseline anti-MOD levels will be measured at Visit 1. During the treatment period, samples will be taken according to the schedule in [Appendix 1: Schedule of Assessments – Main Study](#) to [Appendix 5](#).

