8.5 SAFETY EVALUATION

The assessment of safety will be based mainly on the frequency of AEs, frequency of anti-MOD-4023 antibody development and on the number of laboratory values that fall outside of laboratory normal ranges. Other safety data (e.g. vital signs, special tests, etc.) will be considered as appropriate.

AEs will be listed by treatment group and patient for the treatment phase. AEs will be summarized by presenting, for each treatment group, the number and percentage of patients having any AE, having an AE in each body system and having each individual AE. Any other

OPKO Biologics	Protocol for Clinical Study CP-4-004	Page 97 of 133
Effective Date: Date of final electronic approval		

information collected (e.g. severity or relatedness to study medication) will be listed as appropriate.

Summaries and analyses will be based on treatment-emergent adverse events (TEAE), which are defined as AEs occurring after the first administration of study medication (as recorded on the study discontinuation / end of study CRF) or AEs present before the first dose and ongoing after administration with increased severity. Other AEs (pre-treatment AEs) will only be listed.

If appropriate, laboratory and/or ECG data will be summarized by presenting shift tables using extended normal ranges (baseline to most extreme post-baseline value), by presenting summary statistics of raw data (means, medians, standard deviations, ranges) and change from baseline values and by the flagging of notable values in data listings.

Blood glucose, HbA1c, cortisol, thyroid panel tests and lipid panel tests (with special attention on LpA) will be evaluated using standard descriptive statistics, the number of patients who had values outside normal values, and by listing values considered clinically relevant by the investigator.

Data from other tests (e.g. blood pressure or vital signs) will be listed, notable values will be flagged, and any other information collected will be listed as appropriate. Summary statistics will be given where appropriate.

In addition the number and percentage of patients developing antibodies, including neutralizing antibodies, will be summarized by cohort.

Local tolerability will be summarized based on the investigator's assessments of pain, tenderness, erythema, warmth and swelling which will be done by a scale and predetermined schedule during intensive PK/PD sampling.

The safety analysis will be performed based upon the safety analysis subset.

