3.2 Endpoints

3.2.1 Safety Endpoints

- 1. Incidence of treatment emergent adverse events (TEAEs), serious adverse events (SAEs) and adverse events (AEs) leading to discontinuation
- 2. Incidence of anti-somatrogon antibody formation (including characterization of the antibodies and neutralizing properties)
- 3. Local injection site assessment
- 4. IGF-1 levels and IGF-1 SDS
- 5. IGF binding protein-3 (IGFBP-3) levels
- 6. Parameters of glucose metabolism: blood glucose, fasting insulin level, glycosylated hemoglobin A1c (HbA1c).
- 7. Thyroid status (free thyroxine [FT4], triiodothyronine [T3], and thyroid stimulating hormone [TSH])
- 8. Lipid parameters
- 9. Cortisol levels
- 10. All other hematology and biochemical parameters
- 11. Physical examination
- 12. Vital signs
- 13. Electrocardiogram (ECG) parameters

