9 ANALYSIS OF SAFETY ENDPOINTS

9.1 Adverse Events

AEs will be coded using MedDRA v20.1. TEAEs for each 12 month period will be defined as those that start in each 12 month period and separately for Period V on PEN, which will be cumulative. The denominator used for calculation of AE rates will be the number of patients at the beginning of each period or year. For patients who have gaps in treatment, the events that start in the gap will be included in the prior treatment period. In addition, a summary of AEs for the entire extension period will be provided.

The results will be presented:

- by order of the frequency of AEs by the MedDRA preferred term (PT)
- by severity of AEs
- by the relationship of AEs to the study drug
- and all SAEs

Patient incidence of AEs of special interest will also be summarized overall and by SOC through the entire extension period. The AEs of special interest are:

Adverse Event of Special Interest	MedDRA v20.1 Definition Criteria
Glucose metabolism impairment	Hyperglycaemia/new onset diabetes mellitus (standardized medDRA queries [SMQ]) Full Scope
Thyroid function impairment	Thyroid dysfunction (SMQ) Full Scope
Intracranial hypertension	Increased intracranial pressure disorders (high level term [HLT] - All Paths)
Neoplasias	Malignancy (SMQ) Full Scope
Intracranial aneurysm	Central nervous system aneurysms and dissections (HLT - All Paths)
Immunogenicity (including positive anti-drug antibody and allergic reactions) and Hypersensitivity	Laboratory result parameter: Anti somatrogon antibody or Neutralizing Antibody present, Anaphylactic reaction (SMQ) Narrow Scope, Angioedema (SMQ) Narrow Scope, Hypersensitivity (SMQ) Narrow Scope
Injection site reactions (including lipoatrophy/skin dystrophy)	Injection site reactions (HLT - All Paths) and select PTs (Lack of injection site rotation, Lipoatrophy, Skin hypertrophy, and Skin dystrophy) and PTs containing 'Administration site'
Epiphysiolysis	PT Epiphysiolysis
Haemangioma of skin	PT Haemangioma of skin
Oedema	Oedema NEC (HLT - All paths) and Total fluid volume increased (HLT - All Paths)
Scoliosis	PT Scoliosis
Acute and chronic pancreatitis	Acute and chronic pancreatitis (HLT - All Paths)
Increased Protein kinase	PT Blood creatine phosphokinase increased

Adverse Event of Special Interest	MedDRA v20.1 Definition Criteria
Adrenal cortical hypofunctions	Adrenal cortical hypofunctions (HLT - All Paths)
Myalgia	PT of Myalgia
Myositis	PT of Myositis
Arthralgia	PT of Arthralgia

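### The planned antibody summaries show presence, not new formation: no table counts newly positive patients over previously negative ones

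*SAP*

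**What the plan says.** SAP 3.2.1 lists as its second safety endpoint "Incidence of anti-somatrogon antibody formation (including characterization of the antibodies and neutralizing properties"). Protocol 8.5 states the matching analysis: "In addition the number and percentage of patients developing antibodies, including neutralizing antibodies, will be summarized by cohort".

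SAP 9.2 specifies the tabulation: "The results of the antibody testing will be summarized for each test at each of the OLE and PEN time points tested". It adds titre and specificity for confirmed positives, and a status used to classify growth, IGF-1 and adverse-event results: "A patient is only considered ADA positive at the beginning of the year in which they test positive and for the remainder of the study".

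SAP 9.1 gives a second route. The immunogenicity AESI includes "Laboratory result parameter: Anti somatrogon antibody or Neutralizing Antibody present", together with anaphylaxis, angioedema and hypersensitivity queries, and "Patient incidence of AEs of special interest will also be summarized overall and by SOC through the entire extension period". The general onset rule is that "TEAEs for each 12 month period will be defined as those that start in each 12 month period", and adverse-event denominators are all patients at the start of the period or year.

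On earlier samples, Protocol 5.7.1.5 says "Baseline anti-MOD levels will be measured at Visit 1". Protocol 5.1.2, 5.1.6, 5.1.7 and Appendix 1 show anti-MOD-4023 sampling at Visit 1, week 26 and month 12 for cohorts 1-3, and anti-hGH sampling for the Genotropin cohort. Protocol 5.4.1.1 schedules a pre-dose antibody sample at PEN V1.

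**The concern.** Formation is an incidence: it needs a starting status, a rule for what counts as new, and a denominator of patients who could still convert. SAP 9.2 provides none of these. The same SAP does supply such elements elsewhere: 9.4 gives a denominator and a count-once rule for IGF-1 SDS above 2, and 9.6 defines a baseline for laboratory changes.

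Carry-over is possible by design, because cohorts 1-3 have had 12 months of somatrogon before the first OLE antibody result. The SAP's primary objective is safety in extended treatment, including the move to PEN. A percentage positive cannot show whether longer exposure or the PEN formulation induces antibodies. A high figure could consist wholly of children who converted in the Main Study. In the per-visit results, a flat figure could conceal new cases offset by reversions.

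SAP section 2 says that differences from the protocol's analysis will be documented in the SAP. The move away from the Protocol 8.5 analysis is not recorded.

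**Working it through.** **Step 1: what each planned output yields.**

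| Output | What it gives | What is missing for formation |
|---|---|---|
| SAP 9.2 by time point | Results at each OLE and PEN test | Prior status, definition of new, previously negative denominator |
| Tables 6 and 14.4.1 | Antibody titres, overall and by year | No new-positive count specified |
| AESI summary (SAP 9.1; Tables 4.1 and 20) | Patients with the event, pooled with hypersensitivity terms | Antibody need only be present; denominator is all patients |
| Table 14.3.2.5 | Annual treatment-emergent AESI by preferred term | No onset rule for a laboratory antibody result |
| Rolling ADA status (SAP 9.2) | Classifier for other outcomes | No rule on whether Main Study positives carry over; reversions disappear |

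**Step 2: inputs for the size.** N = 53 patients started the OLE (SAP 4.1). SAP 10.3 refers to OLE years 1-4, so t runs to 4. The documents give no antibody rate, so there is no planned figure to reproduce. The following are assumptions:

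- k patients positive at OLE entry: 0, 10 or 20
- r, the yearly conversion rate among negatives: 0 or 5%
- antibodies persist, and nobody drops out

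**Step 3: formulas.**

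- Any-positive percentage after t years: A = [k + (N − k)(1 − (1 − r)^t)] / N
- New formation among entry-negatives: F = 1 − (1 − r)^t
- Difference: A − F = (k/N)(1 − r)^t

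**Step 4: results at t = 4.** For r = 5%, (0.95)^4 = 0.8145, so F = 18.5%.

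| k | r | A | F | A − F |
|---|---|---|---|---|
| 0 | 0 | 0% | 0% | 0 points |
| 0 | 5% | 18.5% | 18.5% | 0 points |
| 10 | 0 | 10/53 = 18.9% | 0% | 18.9 points |
| 10 | 5% | (10 + 43 × 0.1855)/53 = 33.9% | 18.5% | 0.1887 × 0.8145 = 15.4 points |
| 20 | 0 | 20/53 = 37.7% | 0% | 37.7 points |
| 20 | 5% | (20 + 33 × 0.1855)/53 = 49.3% | 18.5% | 0.3774 × 0.8145 = 30.7 points |

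(Subtracting the rounded percentages in the last row gives 30.8.)

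With k = 10 and r = 0, the by-year results show 18.9% in each of four years: 10 × 4 = 40 positive patient-years and no new case. With k = 10 and r = 5%, they show 22.9, 26.8, 30.4 and 33.9%, while the yearly rate of new formation is a constant 5%.

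**Step 5: direction of the assumptions.** If some entry-positive children revert before their first OLE test, the carried-over part is smaller than shown.

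**The case against.** A reader might infer that every earlier positive is recounted each year throughout the reporting and that new formation is never estimated. The documents do not support that.

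- The AESI summary over the whole extension counts each patient once. Its antibody component equals new formation if nobody is positive at entry.
- Tables 6 and 14.4.1 report overall as well as by year. Recounting affects only the by-visit and by-year results.
- Under the rolling status, patients stay positive once positive, so apart from dropout, first positives appear as year-to-year increases. Reversions cannot mask new cases there; that risk belongs to the per-visit results.
- Main Study antibody information is not ignored. Tables 14.4.2.3, 14.4.2.5 and 14.4.2.8 include the Main Study by ADA status, and Listing 16.2.9.12 covers both phases for CTP-positive patients. With 53 patients, first positives can be derived from listings.
- This SAP covers the OLE only. Formation during the Main Study belongs to a separate analysis that is not available here and cannot be judged. The by-cohort form in Protocol 8.5 could not carry over unchanged, because SAP section 6 pools all patients after OLE year 1.

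These points limit the claim but do not answer it. The AESI criterion admits carried-over positives, is mixed with hypersensitivity terms and uses all patients as denominator. Deriving new positives from listings leaves the rule to be chosen after the data are seen. The absence of hypothesis tests in the OLE does not remove the need to define a listed safety endpoint.

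**Conclusion.** The point holds as a gap in specification. The SAP names antibody formation as an endpoint but plans summaries of presence, and specifies no count of new positives over previously negative patients, for the OLE or for PEN.

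The size is conditional. With 53 patients, persistent antibodies and no new cases, the overstatement is k/53: 0 points for k = 0, 18.9 for k = 10 and 37.7 for k = 20. These values of k are illustrations; the true number positive at OLE entry is not in the documents and could be zero. The change should be made because it is cheap and delivers the analysis that Protocol 8.5 promises. Nothing here shows that the antibody results will be misleading, only that the planned tables could not tell a reader whether they are.

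**What to change.** Keep the per-visit and overall tables and add one table for ADA and for neutralizing antibody. For each OLE year and for PEN, give the number newly positive over the number tested and previously negative, with persistence and reversion in separate rows. Add to SAP 9.2:

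- **Prior status, cohorts 1-3:** from the Main Study samples, Visit 1 to month 12.
- **Prior status, PEN:** from the pre-dose PEN V1 sample plus all earlier results.
- **Genotropin switchers:** their Main Study samples were anti-hGH, and Protocol 5.2 and Appendix 2 schedule an anti-MOD-4023 sample before the switch only after a treatment gap. Those without one should be shown separately, or treated as negative because unexposed, with a sensitivity analysis.
- **AESI note:** state that antibody presence in the SAP 9.1 summary includes carried-over positives.

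The cost is one extra table and a few sentences, using samples already scheduled. The limitation is that some switchers have no baseline sample, so their prior status rests on an assumption.
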